2.2 Secondary Objectives (or Aim)

- Collect preliminary data on outcome

3 INVESTIGATIONAL PLAN

3.1 General Schema of Study Design

3.1.1 Screening Phase

Potential participants will be identified during presentation for treatment at CHOP for an eating disorder. This includes during initial hospitalization for medical stabilization, during outpatient intake assessment, or during the initial medical visit and evaluation. Additionally, potential participants may respond to flyers and tearpads, and independently demonstrate interest in participating by getting in touch with the research coordinators. A member of the study staff will administer a verbal screening over the phone to determine adolescent and parent eligibility. All potential participants who appear to meet inclusion will be provided with information about the clinical trial along with other treatment options. Families who are interested will meet with the study coordinator or research assistants, be provided with more information, and (if inclusion and exclusion criteria are met) scheduled for an intake.

Parental/guardian permission (informed consent) will be obtained prior to any study procedures taking place.

3.1.2 Study Intake

The intake appointment is comprehensive and typically lasts an entire day. The intake battery being used is comparable to one used in other studies by the PI with no ill effects. Families are informed of the length of the intake prior to arrival and it has been well tolerated in the past.

The intake begins with informed consent. Once consent is received, every effort will be made to ensure the family will complete all aspects of the baseline assessment (see Table 1).

Parents and the adolescent will complete a standard questionnaire battery, neuro-psychological assessment, IQ assessment, and a number of behavioral tasks. In addition, the adolescents will complete a diagnostic interview to assess eating disorder symptoms. As part of the intake, the adolescent will be asked to serve and eat a meal. This will be videotaped.

Video-taping will be done using a CHOP approved device. Data will be uploaded to the CHOP server and deleted from the device. All videos will be retained for 6 years and destroyed at that time.

At the end of the intake, the family will meet with their therapist, who will complete the clinical interview and provide information for and schedule the next session. Randomization occurs after the clinical interview.

Consent and assessments will ideally occur in-person; however, if this is not possible then remote consent and assessment will occur. Remote consent will take place on a CHOP-approved video conferencing platform, and study staff will review all sections of the informed consent form with families. Families will be sent a link to our REDCap project with the informed consent form. At the end of the informed consent discussion, families will be asked to e-sign and e-date

in the appropriate sections of the REDCap project. An electronic copy of the informed consent form will also be sent to the families for their records, and a signed version of the informed consent form will be available on REDCap for families to download. Remote assessments will also take place via CHOP-approved video conferencing platforms and will involve all tasks that do not involve physical manipulation of objects and will also not include the buffet challenge. If visits are done remotely, we may ask the parents to weigh their child and share this weight with the study therapist or assessor.

3.1.3 Study Treatment Phase (start of the study intervention)

After the baseline assessment/intake, the family will be randomized to one of three conditions: Family Based Treatment (FBT), Parent Focused Cognitive Remediation Therapy + FBT (CRT_P), or Adolescent Focused Cognitive Remediation Therapy + FBT (CRT_A). Families will have 15 sessions of the assigned treatment and be assessed at 4 additional time points (baseline intake + 4 more is a total of 5 time points). For treatment, all standard clinical procedures will be followed.

In the event of an unforeseen circumstance whereby one's presence at CHOP puts the patient, family, and/or CHOP staff at risk, treatment sessions can be done remotely. All treatment sessions done remotely will take place on a CHOP-approved video conferencing app, such as Vidyo or Skype Business. If treatment sessions are done remotely, we may ask the family to weigh their child and share this weight with the study therapist. A note to file is being made for every treatment session that occurs remotely and will be reported to the IRB and DSMB in a yearly report.

3.1.4 Assessments

Assessments will occur at baseline and then 4 additional times during treatment (total of 5) according to the schedule outlined in Table 1. Assessments will be scheduled within a week of the therapy appointment, ideally on the same day to minimize burden on the family. Questionnaires can be completed on line prior to coming in for the assessment.

In the event of an unforeseen circumstance whereby one's presence at CHOP puts the patient, family, and/or CHOP staff at risk, assessments can be done remotely. All assessment sessions done remotely will take place on a CHOP-approved video conferencing app, such as Vidyo or Skype Business. Remote assessments will involve all tasks that do not involve physical manipulation of objects and will also not include the buffet challenge. If assessments are done remotely, we may ask the family to weigh their child and share this weight with the assessor. A note to file is being made for every assessment that occurs remotely and will be reported to the IRB and DSMB in a yearly report.

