5.1.2 Other Evaluations, Measures

We will collect demographic information from the adolescent and parents. This includes age, date of birth, sex, race/ethnic.

5.1.2.1 *Cognitive flexibility*

Wechsler Abbreviated Scale of Intelligence (WASI;⁶⁰): The WASI is a nationally standardized measure of general intellectual functioning used in clinical, educational, and research settings that scores individuals on four subtests: Vocabulary, Similarities, Block Design, and Matrix Reasoning. We will administer the two subscale version of the WASI to calculate IQ. This is necessary to provide a context in which to understand the results of the neuropsychological testing.

Rey-Osterrieth Complex Figure Test (RCFT;⁶¹): The RCFT measures visual-spatial perception, construction, non-verbal memory, planning, problem solving, and motor function. This test is pen and paper based requiring participants to copy a complex figure. There are two important components to the recreation of the complex figure: recalling it after a brief period of time without priming and the copying it. It is valid to use in adolescents with AN.⁶² It is used as a measure of central coherence. Central coherence has been demonstrated to be impaired in some adolescents with AN.

Delis-Kaplan Executive Functioning Scales (DKEFS);⁶³ The DKEFS is a comprehensive, standardized battery of assessments of executive functioning that can be used with children and adults, ages 8–89 years. It has also been validated for use with adolescents with AN.⁶⁴ Selected subtests administered included: trail making test, verbal fluency test, color-word interference test, and sorting test.

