6 STATISTICAL CONSIDERATIONS

6.1 Primary Endpoint

Aim 1: To identify whether or not it more impactful to add a parent or adolescent component of CRT to standard FBT. To assess if CRT engages the target, we will use mixed 3 (treatment) x 2 (time) Multivariate Analysis of Covariance (MANCOVA): one for adolescents, one for mothers, and one for fathers. The covariate for all analyses is total IQ on the WASI. Dependent variables are as follows: Trails Number-Letter Sequencing, Inhibition, Inhibition/Switching, Correct Response Shifting, Category Switching, or Description 1 or 2 and Shift on the BRIEF-2. We will follow these steps:

1. Conduct omnibus MANCOVA and evaluate significance. If not significant, stop and move to next analysis.
2. If the omnibus test is significant, we will conduct individual 2 (treatment) X 2 (time) Analysis of Covariance (ANCOVA) to determine which dependent variable had significant change, with IQ again as the covariate.
3. Each assessment of the target (DV) will be examined. Results will inform the Go/No-Go Decision as described in Table 6.

These three steps will be repeated for adolescents, mothers, and fathers. We will include all three groups in the initial MANCOVA and follow-up with planned comparisons (ANCOVA) of FBT vs the appropriate CRT condition. In all analyses, we will focus on the within and between-group effects, examining interaction effects are not necessary to evaluate the target. As we have chosen measures demonstrated to change with CRT,^{40,87-90} we will maintain $\alpha=0.15$ for each analysis.⁹¹ We do not expect adolescents whose parents receive CRT or parents whose adolescents receive CRT to demonstrate increases in flexibility. However, should the planned ANCOVAs not be significant, we will be able to explore other possible group differences. Additionally, we will explore the relationship between dependent variables via discriminant analysis. These additional methods to examine the data will not factor into the Go/No-Go decision, but will enhance the depth of our understanding of the data and contribute to our understanding of neurocognition in AN.

Aim 2: To determine the dose of CRT needed to lead to a medium effect size. Some research indicates that ≥ 8 sessions of CRT are necessary for improvement in cognitive flexibility with AN.⁹² It is unknown how many sessions will be needed for significant change in parents of

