6.4 Sample Size and Power

Power analysis Aim 1. In the initial phase of the proposed project (R61), our sample size estimation is based on a mixed MANCOVA design with two repeated measures from baseline to end-of-treatment (EOT; within subjects component) and three groups (CRT_P, CRT_A, and FBT; between subjects component). Based on a review of the literature, we are powering for a medium effect size. Our effect size estimate is Cohen's f statistic.⁹⁸ This effect size estimate is a ratio of variation explained to that unexplained by the model (treatment groups), and is expressed as

follows: $f = \sqrt{\frac{\eta^2}{(1-\eta^2)}}$, where $\eta^2 = \frac{\sigma_{model}^2}{\sigma_{Total}^2}$; proportion of variability due to the model.^{99,100}

Heuristics for small, medium, and large effect sizes are .1, .25, and .4, respectively. We selected an alpha of 0.15, given the nature of the study and the difficulty in recruiting participants from a low prevalence condition. Alpha of 0.15 is essential to provide adequate power for this study.⁹¹ As any analysis powered for a medium effect will also be powered for a large effect, we only highlight the expected medium effect. For all analyses, we specified an $\alpha=0.15$, two time points, and a correlation between measures of .3 (based on unpublished data). The anticipated N accounts for dropouts (i.e., number enrolled will be higher).

Power analysis Aim 2. Using Mplus 7.2,⁹⁴ we conducted a LGCM Monte Carlo simulation with 1000 replications^{94,101-103} to determine power to identify CRT_{P/A} dosage based on a half standard

deviation increase (rate of change; slope) from baseline (effect size) above FBT. With 15 participants in 3 groups across 5 time points, parameter and standard error bias were $\leq 5\%$, confidence interval coverage $\geq 90\%$, and power = 0.59.

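### Remote visits probably leave some Aim 1 D-KEFS scores uncollected, and the planned MANCOVA in its standard form then drops everyone who lacks one of them

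*Combined protocol and SAP*

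**What the plan says.** Remote assessment is open at both Aim 1 time points. For intake, section 3.1.2 says: "Consent and assessments will ideally occur in-person; however, if this is not possible then remote consent and assessment will occur". Section 3.1.4, which covers all five assessments, permits it when attending the hospital would put people at risk. Both sections restrict the content; in 3.1.4 the rule reads: "Remote assessments will involve all tasks that do not involve physical manipulation of objects and will also not include the buffet challenge". Neither says which tasks this excludes.

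Section 5.1.2.1 gives the D-KEFS subtests as "trail making test, verbal fluency test, color-word interference test, and sorting test", without describing materials or administration. Section 6.1 defines the Aim 1 outcome set as "Trails Number-Letter Sequencing, Inhibition, Inhibition/Switching, Correct Response Shifting, Category Switching, or Description 1 or 2 and Shift on the BRIEF-2". The model is a mixed 3 (treatment) x 2 (time) "Multivariate Analysis of Covariance (MANCOVA): one for adolescents, one for mothers, and one for fathers". On adjustment: "The covariate for all analyses is total IQ on the WASI". Section 6.4 identifies the two times as "two repeated measures from baseline to end-of-treatment".

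The omnibus test is a gate. If it is not significant, the single-outcome ANCOVAs are not run for that set of participants, and the results feed the Go/No-Go decision. Section 6 mentions neither remote visits nor missing outcome scores. The only related rule, in section 4.8, concerns people who withdraw and decline the questionnaires. Section 3.3.2 plans about 60 enrolled to give at least 45 evaluable, without defining evaluable.

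**The concern.** The assessment rule and the primary analysis do not fit together. The first accepts that some tasks will be skipped at a remote visit. The second is a multivariate test that, as ordinarily run, needs every outcome at both times. Someone who completes treatment and attends both assessments, one by video, could still contribute nothing to the omnibus test, although several of the outcomes were measured.

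The stake is precision in a small study. Section 6.4 says that an alpha of 0.15 is needed for adequate power, so there is little slack. The sample-size text allows for dropout but not for scores omitted by design. The single-outcome ANCOVAs could recover people whose score on that outcome exists at both times, but only after the omnibus test has passed without them.

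**Working it through.** **1. Which outcomes are exposed.** The documents do not say, so this step is inference.

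| Source of outcome | Physical manipulation of objects? |
|---|---|
| Sorting test (presumably the Description scores) | Probable, from its name |
| Trail making (Number-Letter Sequencing) | Possible, if a paper form is used |
| Verbal fluency, color-word interference | No sign of it |
| BRIEF-2 Shift | No; questionnaires can be done online |

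One affected outcome in the model is enough for what follows.

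**2. What the standard analysis does.** A trial run of a seven-outcome MANOVA with one covariate and 45 rows, with one outcome blank in 9 rows, used 36 rows. The other six scores in those 9 rows were discarded.

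**3. The plan's sample size.** 60 enrolled and 45 evaluable imply a loss of 1 − 45/60 = 25%, and 45/0.75 = 60. This checks consistency only, since the 25% comes from the same two figures. The 45 agrees with three groups of 15 in the Aim 2 power text.

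**4. Illustrative loss.** Let r be the chance that a given visit is remote (assumed; no rate is given).
- Independent visits: complete cases = 45 × (1 − r)².
- Same people remote at both visits, or only one of the two visits ever remote: 45 × (1 − r).

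| r | Independent | Fully clustered, or one visit only |
|---|---|---|
| 10% | 45 × 0.81 = 36.5 | 45 × 0.90 = 40.5 |
| 20% | 45 × 0.64 = 28.8 | 45 × 0.80 = 36.0 |
| 30% | 45 × 0.49 = 22.1 | 45 × 0.70 = 31.5 |

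**5. Illustrative power.** The text available gives no Aim 1 power figure to reproduce. As a single-outcome approximation, take the section 6.4 inputs (f = 0.25, alpha = 0.15, m = 2 times, correlation ρ = 0.3), three groups and one covariate, and use the noncentral F distribution. For the between-group effect λ = f²Nm/(1 + (m − 1)ρ); for within-person and interaction effects λ = f²Nm/(1 − ρ). Error degrees of freedom are N − 3 − 1. At N = 45, λ is 0.0625 × 45 × 2/1.3 = 4.33 and 0.0625 × 45 × 2/0.7 = 8.04.

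| N | Between | Within | Interaction |
|---|---|---|---|
| 45 | 0.64 | 0.91 | 0.85 |
| 36 | 0.56 | 0.85 | 0.77 |
| 29 | 0.48 | 0.79 | 0.69 |
| 22 | 0.41 | 0.69 | 0.58 |

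The multivariate test on seven or eight outcomes will differ in level. The table shows only how power falls with the number analysed.

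**The case against.** The best reply is that this is a contingency of unknown frequency. In-person assessment is preferred, section 3.1.4 confines remote assessment to unforeseen risk, section 3.1.2 promises effort to complete the whole baseline battery, and section 9.5 lets hospitalised families split theirs. Complete-case deletion is a default of the method, not a written rule. The alternatives in the outcome list leave it unclear whether the Description scores must enter the model at all.

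Much of this stands, and it rules out several stronger readings that a reader might infer:
- **That remote visits certainly remove D-KEFS outcomes.** The tasks are not named. Sorting is a fair inference; trail making is weaker, because marking a form is not clearly manipulation of objects and forms could be mailed.
- **That a whole family is lost.** The analyses are separate for adolescents, mothers and fathers. A family is lost only if the remote visit covers all its members.
- **That the analysed sample will be much smaller.** No remote rate is given and clustering reduces the loss. If evaluable already means usable for Aim 1, subtracting from 45 counts the loss twice.
- **That the loss is non-random or biases the comparison.** Loss driven by periods of restricted access need not differ between randomised arms. The documents show nothing either way.

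What the reply does not supply is a catch-up for remote visits or an analysis that uses the scores obtained. The general promise at baseline and the split assessment for inpatients do neither, and section 4.8 covers only withdrawals.

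**Conclusion.** The concern holds in a limited form. Remote assessment at baseline or end of treatment probably omits the sorting scores and possibly trail making. If an omitted score is in the outcome set, the MANCOVA in its standard form excludes that person and discards the remaining scores from the test that gates Aim 1. With 10% or 20% of each visit remote, independently, about 36 or 29 of 45 remain, against about 40 or 36 if remote use is fully clustered. Under the approximation above, between-group power falls from 0.64 to 0.56 or 0.48 in the independent case.

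This rests on four assumptions: at least one included outcome is omitted remotely; the MANCOVA is run on complete cases; the 45 does not already allow for the loss; and the remote rate lies in the range shown. Aim 2 is not affected in the same way, because its maximum-likelihood growth model can use incomplete records.

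**What to change.** 1. **Section 6.1.** Replace the complete-case analysis with one that uses all available scores, by either of two routes. (a) Multiply impute the missing subtest scores, then run the planned MANCOVA; the intermediate D-KEFS assessments in Table 1 can help predict them. (b) Fit a likelihood-based repeated-measures model with a structured outcome-by-time covariance. An unstructured one is not realistic: 7 outcomes at 2 times need 14 × 15/2 = 105 covariance parameters and 8 outcomes need 16 × 17/2 = 136, for about 45 people. With either route, use per-outcome mixed models in place of the follow-up ANCOVAs. Both routes assume that missingness is explained by the observed data, which should be stated.
2. **Sections 3.1.2 and 3.1.4.** Name the tasks omitted remotely. Where attendance is possible, complete them in person: before randomisation for baseline, since section 3.1.2 places randomisation after the intake interview, and within the existing 14-day window of section 3.1.5 for end of treatment.
3. **Assessment mode.** Remote assessments already require a note to file. Enter the mode in the database and use it only in a sensitivity analysis of subtests given in both modes. It cannot be estimated for a subtest never given remotely, and at end of treatment it arises after randomisation, so it does not belong in the main model.

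The cost is revised wording, one database field, slightly more analysis work and a short extra test session for some families. Where attendance remains unsafe, the catch-up will not happen and item 1 carries the weight.

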3.1.5 End of Treatment Evaluation

The End of Treatment Evaluation will occur within 14 days of treatment end. It will mirror the intake and include the measures noted in Table 1.

3.1.6 Post Treatment Follow-up

After finishing the study, participants will receive questionnaires via link in email (for RedCap) and/or paper versions mailed to them. These will be sent approximately 3- and 6-months after completing the study. Families will also have the option to receive an additional 12 FBT sessions during this time. The study team will also complete medical chart reviews during these two follow-up periods. Should an adolescent turn 18 years of age during post treatment follow-up, the study team will request that the adolescent makes an appointment for reconsenting after turning 18. This appointment can take place at any CHOP affiliated facility (e.g., Roberts Center for Pediatric Research, Adolescent Medicine Specialty Care Center, etc). If the adolescent is unable or unwilling to reconsent, they will not be sent questionnaires for completion. Parents, however, will be sent questionnaires.

3.2 Allocation to Treatment Groups and Blinding

The study statistician will facilitate the sequential randomization of participants employing a covariate-adaptive randomization method (using open source free software; OxMaR)⁵⁷ that ensures an equal distribution of males across the three conditions.^{58,59} Minimization works by re-calculating the probability of allocation to the treatment and control groups after each new participant enters the cohort. The probability of assignment will depend on stratification by sex and age to assure that males have an equal probability of assignment to the different conditions, something that is not guaranteed with simple random assignment. The algorithms for doing this will be programmed ahead of time, study team members will enter the sex and age of participant into the program in order randomize them to groups. The statistician will not have access to any PHI.

Research assistants conducting assessments will be blinded to treatment condition at all time points.

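### Allocation is minimised on sex and age, but the Aim 1 models adjust only for IQ; if either factor is prognostic, the between-group tests, chiefly in adolescents, will be conservative

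*Combined protocol and SAP*

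**What the plan says.** **Allocation.** Protocol section 3.2 describes minimisation with the OxMaR software, the aim being to spread males evenly over the three arms. The factors are sex and age: "The probability of assignment will depend on stratification by sex and age to assure that males have an equal probability of assignment". In practice "study team members will enter the sex and age of participant into the program in order randomize them to groups". The participant is in the singular, and I read it as the adolescent.

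**Analysis.** Section 6.1 plans three sets of Aim 1 analyses, "one for adolescents, one for mothers, and one for fathers". On adjustment it says "The covariate for all analyses is total IQ on the WASI", and the follow-up ANCOVAs are run "with IQ again as the covariate". On the effects of interest it says "we will focus on the within and between-group effects, examining interaction effects are not necessary to evaluate the target". No section adds sex or age to an Aim 1 model or gives a reason for omitting them.

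**Power.** Section 6.4 bases the sample size on a "mixed MANCOVA design with two repeated measures from baseline to end-of-treatment", with three groups, a medium effect (f = 0.25) and a correlation of .3 between the two measurements. On the error rate it says "We selected an alpha of 0.15, given the nature of the study", and it calls that level essential for adequate power. Section 3.3.2 expects about 60 enrolled and at least 45 evaluable, that is 45/3 = 15 per arm.

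**The concern.** Minimisation makes the arms more alike on sex and age than simple randomisation would. The true sampling variation of an arm difference then no longer contains the part due to those two factors. A model that omits them still counts their variance as residual error. Where they predict the outcome, the estimated standard error is larger than the variability the design actually produces, and the test rejects less often than its nominal level.

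That would matter here because the trial is small, alpha was relaxed to 0.15 to gain power, and Aim 1 feeds the Go/No-Go decision (sections 6.1 and 10). A test that runs below 0.15 gives back part of what the relaxed alpha was meant to buy.

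**Working it through.** **No stated figure to reproduce.** The available text gives no Aim 1 power; a table may have been lost in text extraction, and I do not count that against the plan. The only stated power, 0.59, is for the Aim 2 growth-curve simulation.

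**Inputs from the documents.** N = 45 evaluable, 15 per arm (3.3.2); f = 0.25, alpha = 0.15, two time points, correlation .3 (6.4); IQ as the only covariate (6.1).

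**Assumed.** R2, the share of outcome variance that sex and age explain: 0.05 to 0.20 in check 1, 0.05 to 0.25 in check 2. All results are univariate approximations to the MANCOVA.

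**Check 1: three-group between-group F test.** Noncentrality is f² × N × m / (1 + (m − 1) × rho), with m = 2 time points. That is 0.0625 × 45 × 2 / 1.3 = 4.327. The IQ-only model has 45 − 3 − 1 = 41 error df. Adding sex and age leaves 39 and divides the noncentrality by (1 − R2), where R2 refers to the mean over the two times.

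| Model | R2 | Noncentrality | Error df | Power | SE ratio 1/√(1 − R2) |
|---|---|---|---|---|---|
| IQ only | – | 4.327 | 41 | 0.636 | – |
| + sex, age | 0 | 4.327 | 39 | 0.635 | 1.00 |
| + sex, age | 0.05 | 4.555 | 39 | 0.654 | 1.03 |
| + sex, age | 0.10 | 4.808 | 39 | 0.673 | 1.05 |
| + sex, age | 0.20 | 5.409 | 39 | 0.716 | 1.12 |

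**Check 2: baseline-adjusted comparison of one CRT arm with FBT, 15 v 15, half-SD gain.** Without sex and age, the residual variance is 1 − 0.3² = 0.91, SE = √(0.91 × 2/15) = 0.348, and power at two-sided 0.15 is 0.49. Baseline adjustment already absorbs part of any stable sex or age effect. If the two factors explain the same R2 at both times, the residual variance becomes (1 − R2) × [1 − ((0.3 − R2)/(1 − R2))²].

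- R2 = 0.05: 0.95 × (1 − (0.25/0.95)²) = 0.884. SE ratio √(0.91/0.884) = 1.01; power 0.497.
- R2 = 0.25: 0.75 × (1 − (0.05/0.75)²) = 0.747. SE ratio √(0.91/0.747) = 1.10; power 0.546.

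**Check 3: simulated type I error.** Three-arm minimisation on sex and three age bands, N = 45, 3000 replications per cell. The probability of 0.8 for the best arm, the 10% males and the age bands are assumptions. Monte Carlo SE is about 0.007.

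| R2 | IQ only | IQ + sex + age |
|---|---|---|
| 0 | 0.157 | 0.158 |
| 0.05 | 0.135 | 0.143 |
| 0.10 | 0.128 | 0.146 |
| 0.20 | 0.115 | 0.151 |

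Simulated power moves the same way: 0.635 v 0.651 at R2 = 0.05, and 0.610 v 0.691 at R2 = 0.20.

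**The case against.** The strongest reply is that the loss is conditional and may be small.

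- **No figure for R2.** The documents do not say how strongly sex or age relates to any outcome given IQ. At R2 = 0 nothing is lost. This stands.
- **Age-normed scores are possible.** Section 5.1.1 collects parental birth dates because the neuropsychological assessment needs them, section 5.1.2.1 describes the DKEFS as standardised over ages 8 to 89, and section 9.2.1 mentions both raw and standard scores. Section 6.1 does not say which are analysed. Norming would remove most of the age variance; raw scores over ages 12-18 could keep it. This stands as a limit on size.
- **Parent models.** Two of the three sets of analyses are of parents, with parent sex constant in each. Nothing suggests that a child's sex and age explain much of a parent's test score. This stands.
- **Within-subject tests.** Stable additive effects of sex and age cancel in the time comparison. This stands.
- **Validity.** Simulated error under the IQ-only model is at or below nominal apart from Monte Carlo noise, so false Go decisions are not increased. This stands: the issue is efficiency and agreement between analysis and design.

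A reader might infer that standard errors are certainly too large throughout Aim 1, and in the Aim 2 growth model too. The documents do not support that. The effect needs prognostic factors, and in the growth model stable level differences go to the intercept rather than to the slope that bears on dose; no Aim 2 loss has been shown.

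A reader might also apply the full factor 1/√(1 − R2) on top of the baseline-adjusted variance in check 2, which gives SE ratios of 1.03-1.15 and power of 0.503-0.574 for R2 of 0.05-0.25. That counts the stable part twice. With a correlation of .3, R2 = 0.25 already leaves only 0.05 of the between-time correlation for IQ and every other stable trait, so the upper end is generous.

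**Conclusion.** The mismatch between sections 3.2 and 6.1 is plain on the text. Its consequence is conditional: if sex or age predicts the outcome given IQ, the between-group tests, chiefly in the adolescent model, are conservative. Under the assumed R2 of 0.05 to 0.20, the three-group between-group test loses about 2 to 8 power points (0.636 against 0.654-0.716) and its simulated type I error is 0.135 to 0.115 instead of 0.15. In the baseline-adjusted two-arm comparison the loss is about 1 to 6 points for R2 of 0.05 to 0.25 (0.49 against 0.497-0.546). The direction is secure once R2 exceeds zero. The size is not, because R2 and the score type are unknown.

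**What to change.** In section 6.1, prespecify the adolescent's sex and age, in the form used for the minimisation, as covariates beside baseline WASI IQ in the adolescent Aim 1 MANCOVA and its follow-up ANCOVAs. If the sponsor prefers to omit them, give the reason. State whether raw or age-scaled scores are analysed, since that largely decides how much adjusting for age can gain. Including the two factors in the mother and father models, for consistency with the allocation, is optional. Extending them to the Aim 2 growth model is not required.

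The cost is a sentence or two of plan wording and two error degrees of freedom per outcome. By formula that is about 0.1 power point if the factors are not prognostic (0.636 to 0.635). In the MANCOVA each added covariate also brings one coefficient per outcome. No new data are needed, because both variables are already entered at randomisation.
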